### **Our Specific Aims are to:**

1. Determine whether individuals with mood disorders treated with a health plan-level CCM demonstrate improved health outcomes and quality of care at 12 months compared to those who are mailed educational material alone (Educational Control-EC).

Our **primary hypothesis** is that compared to EC, the mood CCM will result in a) reduced mood symptoms in 12 months, or b) improved health-related quality of life.

Our secondary hypotheses is that patients receiving CCM vs. EC will have improved guideline-concordant care (e.g., mood disorders treatment, cardiometabolic monitoring), reduced hospitalizations, and improved work productivity within 12 months.

2. To support subsequent CCM dissemination by identifying key organizational, provider, and patient characteristics associated with CCM engagement and outcomes.
3. To conduct a cost-effectiveness analysis of CCM versus EC on changes in patient utilities over 24 months and apply findings to develop a business case for CCMs in smaller practices.

This proposed R18 addresses **AHRQ's research demonstration and dissemination priorities**, particularly around prevention and care management, with an emphasis on vulnerable groups including more rural populations (the majority of Aetna enrollees are seen in smaller practices). It also confronts unanswered organizational and financial questions raised by a recent **AHRQ report** ("A National Agenda for Research on Collaborative Care"). As one of the first cross-diagnosis CCM-based implementation studies focused on small practices, this groundbreaking study is informed by an extensive partnership with a network-model health plan (Aetna). The study also applies a novel implementation framework (REP) in which the CCM is delivered by existing providers. In addition to the specific importance of this practice-research partnership to further implement CCMs among small practices at the health plan level within a natural experiment setting, this study will contribute to the evolution of the business case for CCMs in general, enhance the utility of plan-level panel management focused on vulnerable populations across different treatment settings, and inform remote technologies that will facilitate emerging healthcare initiatives (e.g., accountable care organizations, health IT).

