**Aim 2 analyses are considered exploratory** but will be used to gain insight into the mechanisms by which CCM impacts patient outcomes. We will first explore the strength and direction of the association between patient-level CCM engagement (API-D scores- see section C.5.f) (119) on changes in outcomes (SF-12, PHQ-9 and ISS scores) by adding patient-level API-D scores to the aforementioned linear mixed-effects models from Aim 1. We will also be run exploratory analyses in which we add key organizational factors (e.g., non-solo practice, practice type-primary care vs. behavioral health, presence of non-MD clinical staff, EMR use, ownership), and other patient factors (e.g., demographics, comorbidities) in the models specified in Aim 1. In secondary analyses we will also incorporate the number of additional optional sessions covering supplemental modules completed by the patient (Section C.5.d).

**Aim 3: Both a payer and societal-based cost-effectiveness analysis (CEA) will be conducted.** A CEA from the payer perspective will involve comparison of utilization costs of health service providers including CM's time ascertained from time-motion survey. A societal perspective will add non-health care costs incurred by patients including time and transportation. Generalized Linear Models with log link functions will be used to correct for heteroscedasticity and reduce the impact of outliers (131). The incremental effectiveness of CCM compared to EC will be measured by changes in health utilities, assessed using a method described by Zivin (132) and Brazier (133) which translates six of the SF-12 items to changes in health utility (SF-6) based on responses to standard gamble questions given by community members regarding all combinations of possible health states. Cost-effectiveness ratios will be calculated based on the difference in per patient costs and effectiveness of CCM versus EC. To quantify uncertainty around these ratios, a standard nonparametric

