bootstrapping approach will be employed. For the business case, additional analyses will be conducted in which changes over time in utilization and costs of inpatient, ER, and outpatient services (medical, psychiatric) will be compared between patients in the CCM or EC arms over a 2-year period, in order to determine the time dynamics by which the CCM led to changes in health care costs. Additional cost analyses will take into consideration the return-on-investment of the CCM and changes in enrollee turnover (134).

**C.5.h. Business plan development (Aim 3).** The business case development plan is based on our Enhanced REP framework (73) and informed by the work by Leatherman and colleagues (also see Appendix for submitted paper on business case). In brief, a business case for the CCM exists if the Aetna realizes a financial return on investment or other positive impact on organizational function or sustainability within a “reasonable” time frame (134). Other positive impacts beyond the potential cost savings from implementing CCM include revenue-based from the payer perspective (i.e., value added to payers when the health plan offers CCMs in terms of improved enrollee health and access to care). We chose 2 years as the time frame for outcomes in this study because prior research on CCMs has not found a return-on-investment within one year (3), and 2 years is below the average tenure of an Aetna enrollee. From a business case standpoint, attrition from the health plan may attenuate savings from the initial investment, and our analysis will implicitly account for this by only counting within-plan utilization costs. Enhanced REP addresses organizational and financial incentives (Table 6) designed to inform the CCM return-on-investment (73) and will lead to the development of a reimbursement model for CCMs. Preliminary stages for business case development (134), including (a) the implementation of a program (CCM) shown to improve patient health (135), (b) establishment of quality and cost indicators aligned with existing national initiatives (e.g., ACOs), and (c) identification of a health plan champion and consultant team have been completed. The remaining years (3-5) will be devoted to refining and marketing the business plan, which will include a CCM reimbursement strategy.

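### In the societal cost-effectiveness analysis, plan-only health-care costs end at disenrolment while utilities run to 24 months, and nothing adjusts for time enrolled

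*Combined protocol and SAP*

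**What the plan says.** Aim 3 (section II) is a "cost-effectiveness analysis of CCM versus EC on changes in patient utilities over 24 months". C.5.g (Aim 3) plans a payer and a societal version, using log-link generalized linear models and ratios built from cost and effect differences per patient. On the second version it says "A societal perspective will add non-health care costs incurred by patients including time and transportation".

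Utilization and cost data come from the plan's eTUMS and claims databases (C.5.f). The patient survey adds participants' own spending on drugs and co-pays, plus travel and time. Utilities come from telephone surveys, the last at 24 months (C.5.f). No section says that surveys stop when a patient leaves the plan.

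Disenrolment is addressed in two places. C.5.h says "From a business case standpoint, attrition from the health plan may attenuate savings from the initial investment", and then that "our analysis will implicitly account for this by only counting within-plan utilization costs". The last paragraph of C.5.g (Aim 3) says "Additional cost analyses will take into consideration the return-on-investment of the CCM and changes in enrollee turnover", without a method. On horizon and tenure, C.5.h says "We chose 2 years as the time frame for outcomes in this study" and gives as one reason that "2 years is below the average tenure of an Aetna enrollee".

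**The concern.** A cost-effectiveness ratio needs costs and effects over the same period. From the societal viewpoint, an admission paid for by a later insurer is as real a cost as one paid for by this plan. Under the plan as written it has no data source, while the patient's utility is still measured.

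Two consequences follow. If patients leave at the same rate in both arms, the dollar cost difference shrinks while the effect difference does not. If exit differs by arm, part of the apparent cost difference reflects time enrolled and not use of care. Unequal exit is plausible: benefits are provided through employers (C.1), and CCM is hypothesised to improve work productivity (section II), which could affect who keeps coverage. The plan itself intends to look at "changes in enrollee turnover". The results feed the reimbursement strategy in Table 6.

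**Working it through.** The documents state no 24-month cost, exit rate or cost power, so there is no planned figure to reproduce. The check has two parts.

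**1. The two sides of the societal ratio**

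| Component | Source | Observed after disenrolment? |
|---|---|---|
| Inpatient, ER and outpatient care | Plan databases (C.5.f) | No source named |
| Patients' own costs, travel, time | Patient survey (C.5.f) | Yes, if surveys continue |
| Utilities | Patient survey to 24 months (C.5.f) | Yes, if surveys continue |

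Coverage of at least 6 months is required at entry (C.5.b), but no continuous-enrolment rule applies during follow-up. All analyses are by intention to treat (C.5.g), so leavers stay in the comparison. The cost model has no stated offset for enrolled time and no censoring weight. The missing-data paragraph of C.5.g names neither costs nor disenrolment.

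**2. Illustration; every exit rate is an assumption**

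Assume a constant monthly cost, the same in both arms, and exit spread evenly over 24 months. A share f leaves, and leavers are observed for half the period on average:

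observed share of 24-month cost = 1 − f/2

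| Exit EC | Exit CCM | Observed EC | Observed CCM | CCM/EC (true value 1) |
|---|---|---|---|---|
| 30% | 20% | 0.85 | 0.90 | 0.90/0.85 = 1.059 |
| 20% | 30% | 0.90 | 0.85 | 0.85/0.90 = 0.944 |
| 20% | 20% | 0.90 | 0.90 | 1.000 |
| 40% | 40% | 0.80 | 0.80 | 1.000 |

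Unequal exit gives a false CCM excess of 5.9% or, reversed, a false saving of 5.6%. Equal exit of 20% or 40% lowers totals by 10% or 20%. If the arms truly differ in monthly cost, equal exit shrinks the dollar difference by the same percentage and leaves the ratio of costs unchanged.

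A constant exit hazard gives similar results. With hazard h = −ln(1 − f)/24, expected enrolled months are (1 − exp(−24h))/h. For f = 20% this is 21.51 months, a shortfall of 1 − 21.51/24 = 10.4%. For f = 30% it is 20.19 months. EC 30% against CCM 20% gives 21.51/20.19, about 1.07.

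Under the same assumptions, cost per enrolled month gives a ratio of 1.00 in every case.

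Timing can matter too. C.5.h says earlier research found no return within one year. If savings fall only in year 2 and 20% leave evenly over 24 months, 10% have left by month 12 and lose all their savings. The other 10% leave during year 2 and lose half on average. The loss is 10% + 5% = 15% of savings, even with equal exit.

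**The case against.** The strongest reply concerns scope. The within-plan sentence is framed from the business-case standpoint. For the plan's return on investment, a former member's care costs nothing, and an arm difference in exit is a real difference in plan spending. This stands. A reader might infer that counting within-plan costs is wrong throughout and understates cost; for the return-on-investment analysis it does not.

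A reader might also infer that the plan sets months after exit to zero. The documents do not say whether those months are zero, missing or censored. What can be said is that a per-patient sum of plan costs adds nothing for them, and a complete-looking total would not be flagged as missing.

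The payer analysis is arguable. If the payer is this plan, care funded elsewhere lies outside the perspective. Against that, C.5.f prices services at standardized Medicare-fee values, which points to resource use more than to the plan's ledger. The documents do not settle it.

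The general missing-data methods and the promised look at turnover are relevant, but neither gives a rule for costs after exit. Mean tenure above 2 years does not exclude substantial exit within 2 years.

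On size, the reply is right that no exit rate is available. A dollar figure would also be unsafe. Table 2 covers behavioral health cost over six months only, while Aim 3 covers medical and psychiatric care at standardized prices. Flat monthly cost is doubtful after a hospitalization: pilot EC cost fell from $6,048 to $3,492. If later months are cheaper, exit loses less than the illustration suggests. Finally, C.5.j calls the cost-effectiveness work exploratory and underpowered, which limits the weight of the point without removing it.

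**Conclusion.** The concern holds for the societal analysis. As written, health-care costs can be observed only while the patient is enrolled, effects run to 24 months, and no step reconciles the two periods. This shrinks the dollar cost difference, and could bias the cost-effectiveness ratio further if exit differs by arm.

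Neither size nor sign can be derived from the documents. The figures of about 6% for a ten-point difference in exit, and about 10% for equal exit of 20%, rest on assumed exit rates, evenly spread exit and constant monthly cost. They show scale only and do not support a claim that the result will be biased in a particular direction.

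For the payer analysis the finding is narrower: its target is undefined. For the business case there is no fault in the within-plan rule. Because the analysis is exploratory, this is a change that should be made, not one that threatens the trial's primary conclusions.

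**What to change.** - **Societal analysis:** treat disenrolment as censoring of costs. Use inverse-probability-of-censoring weighted 24-month costs, or cost per enrolled month with time enrolled as an offset. The offset assumes a steady monthly cost; weighting by interval does not, but needs exit to be explained by measured covariates.
- **Payer analysis:** state whether the target is this plan's spending (within-plan totals) or 24-month resource use, and give the censoring-adjusted result as a sensitivity analysis.
- **Business case and return on investment:** keep within-plan totals.
- **Reporting:** give enrolled months and exit by arm, and state that surveys continue after a patient leaves the plan, if that is intended.

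The cost is a little more analysis and wider intervals. Enrolment dates must be obtained from the plan; the documents do not say that they are part of the data export.

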**Table 6: Enhanced REP Framework Business Case Development Steps by Year and Study Aim**

Enhanced REP Phase	Incentives Components Informing Business Case
Pre-conditions (Years 1-2)	Identify health plan’s current priorities, and organizational barriers and facilitators to implementing CCM (Aim 2). Establish, publicize measureable CCM outcomes (Aim 1), aligned with existing measures (e.g., ACO quality, measures: cardiometabolic, mood stabilizer use, and hospitalizations (111))
Pre-Implementation (Years 1-5)	Identify health plan, provider champions who mobilize support for CCM (Aetna, consultant team) Identify successfully implemented CCM components across plan (e.g., existing health IT-eTUMS)
Implementation (Years 3-5)	Consultant team reviews EBP business case, holds regular calls to develop business plan based on study findings (Aim 3- CEA). Propose reimbursement strategies (e.g., billing codes, bundled payments through ACOs- See Appendix) and highlight trade-offs with initial investment, long-term ROI
Maintenance and Evolution (Years 4-5)	Market business plan to sustain CCM beyond health plan to other national leaders in public, private sector (Dissemination plan). Leverage CCM with existing federal programs that are reimbursable (ACOs, health home models); continue publicizing CCM, find consumer stories re: CCM benefits

**C5.j. Potential Study Limitations.** This study involves a number of strengths, including a groundbreaking health plan- academic partnership, comprehensive data sources, and emphasis on smaller and solo practices. Nonetheless, there are key limitations of this proposed design to consider. The focus on mood disorders potentially limits the immediate reach of this novel approach to implement CCMs for other chronic conditions. However, mood disorders have been identified by Aetna as priority conditions, and represent the most common and costly mental disorders in routine practice (136). In addition, while many persons with mood disorders are privately insured under network-model HMOs such as Aetna (137), the potential generalizability of this study is restricted to insured individuals. This study nonetheless complements a number of initiatives in the public sector that are currently being implemented to increase the uptake of CCMs for mental disorders such as health homes (10). Site providers will not be blinded to treatment assignment because CCM management and guideline supports require care manager-provider communication. Guideline concordance based on CM-provider coordination was found to be a key factor to the improvement of outcomes in the CCM (98). Finally, the cost effectiveness analysis is exploratory and not fully powered, but will nonetheless, provide valuable information for organizations considering its further adoption.

**C.5.k. Timeline and Organization.** The first 6 months of the study will involve staff training and finalization of recruitment procedures (Figure 3). Once recruitment and enrollment begin in month 6, the CCM will be implemented throughout all study locations. Based on pilot studies recruitment is anticipated to last 18 months, hence allowing for ample time to recruit patients with either bipolar disorder or depression. Years 3-5 will be devoted to follow up data, business case, as well as other dissemination and implementation activities.

**Figure 3: Study Timeline**

Study Month	1-6	7-12	13-18	19-24	25-30	31-36	37-42	42-48	49-54	55-60
Start-Up										
Patient Enrollment										
Patient Assessments										
Provider/org. Data Collection										
Business Case Development										
Final Analyses & Dissemination										

Organizational relationship between investigator team and Aetna group (also see letter from [name]): Aetna is providing support for the study organization through in kind contribution of effort by three key personnel ([name], [name], and [name]) and the establishment of a Joint Operating Committee to facilitate project operations, care management infrastructure, and the informatics system. Aetna has used joint operating committees successfully in past clinical trials involving academic partnerships (e.g., 1R01DA029716; 1R01DA026414). Specifically, [name] and [name] will serve as Co-Chairs of the Joint Operating Committee which will include both Aetna leaders and study investigators of the project, and will have oversight of all aspects of the project. The Committee will employ three function-oriented subcommittees with one co-chair from Michigan or Harvard and one from Aetna who will oversee: CCM Implementation (Co-chairs: [name], [name]), Patient Enrollment and Data Collection (Co-chairs [name], [name], and [name]), and

Data Management and Analysis (Co-chairs [name], [name] and [name]). The Aetna co-leaders from each subcommittee have oversight over the Aetna personnel responsible for the respective functions. All Aetna data will be available for audit by the Committee, and additionally we will utilize a Data Safety and Monitoring Board comprised of scientists separate from this project who will have similar access. Thus our joint operating structure provides both the data monitoring oversight and the line authority control required to ensure the successful implantation of this project. [name], Clinical Specialty Programs Head for the Aetna Behavioral Health, will oversee and manage the clinical operations and fidelity of the CCM implementation, including care manager and research associate supervision. This will include weekly meetings with the care managers' supervisors to review the pilot's key operational performance and fidelity metrics to ensure adherence to pilot workflows and protocols. He will coordinate with leadership to support overall implementation. [name] will support [name] and have responsibility for planning, execution and finalization of the project according to identified timelines and within budget. [name], Head of Aetna Behavioral Health Clinical Program Informatics, will be responsible for managing and aggregating the necessary outcome measures defined for the study (See Budget Justification).

**C.5.I. Dissemination and Generalizability.** A dissemination strategy that ensures awareness and knowledge of research findings among clinicians, consumers, and policymakers, is an initial step to realizing the promise of this project, and fostering the potential generalizability of the findings. Once the intervention is completed and if proven effective, the Enhanced REP Framework will be applied to train other Aetna care managers in CCM. There are three stages of REP (packaging, training, and technical assistance). The CCM package will consist of a web-based therapist manual, administrator overview, and consumer handouts. Care managers as part of this study as well as providers with a high uptake score will be encouraged to become mentor-trainers who can provide training for other providers in the CCM. A refined technical assistance program based on study findings will be incorporated into the business plan for sustaining CCMs across Aetna and elsewhere. Study findings as well as the business plan will be disseminated through web sites, press releases, national conferences, policy briefs, as well as traditional forms of academic scholarship. If proven effective, the telephonic mood disorders CCM program may also potentially be scaled up to larger practices, notably through the use of technologies such as telemedicine or web-based portals independent of the care manager's physical location. At least five manuscripts will be produced based on study aims including: 1) description of the Aetna CCM, and 2) CCM main outcomes, 3) mechanisms of CCM effects, 4) cost and utilization of CCM, and 5) the updated CCM business plan. A policy brief based on study findings will be disseminated to consumer and policy groups (e.g., AHRQ, CMS, Depression and Bipolar Support Alliance, National Alliance for the Mentally Ill, Primary Care Associations, National Council for Community Behavioral Healthcare), as well as to policymakers who have an interest in mental health.

1. U.S. Department of Health and Human Services. U.S. Department of Health and Human Services (HHS) Inventory of Programs, Activities and Initiatives Focused on Improving the Health of Individuals with Multiple Chronic Conditions (MCC): Compiled by the HHS Interagency Workgroup on Multiple Chronic Conditions under the direction of [name], MPH, Deputy Assistant for Health (Science and Medicine), Office of the Assistant Secretary for Health; September 2011 Contract No.: Document Number|.

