- c. Recent (past 6-month) hospitalization for an acute psychiatric or partial hospital unit with a manic or depressive episode and confirmation of mood disorder diagnosis at discharge (52).
- d. Ability to speak and read English and provide informed consent

4. The research associate (RA), who will be external to Aetna to maintain separation of care management and program evaluation, and will be blinded to randomization assignment. (S)he will be trained by Aetna on their well-established call implementation program across time zones (**Section C.5.c**) and by study investigators in human subjects risk reduction procedures used in prior studies (8, 50) that will minimize risk while not compromising study internal validity (8). The initial assessment (described below) will include a brief survey baseline factors, including demographics, employment, whether they were the Aetna enrollee or a family member, and primary

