**Figure 2: Implementation of Mood CCM across Health Plan, Practices, and Patients**

clinician who treats their mood disorder (i.e., prescribes psychotropic medications). Comorbidities will be ascertained from Aetna eTUMS chart reviews conducted by the RAs.

program evaluation, and will be blinded to randomization assignment. (S)he will be trained by Aetna on their well-established call implementation program across time zones (**Section C.5.c**) and by study investigators in human subjects risk reduction procedures used in prior studies (8, 50) that will minimize risk while not compromising study internal validity (8). The initial assessment (described below) will include a brief survey baseline factors, including demographics, employment, whether they were the Aetna enrollee or a family member, and primary

**C.5.c. Existing Aetna Infrastructure Used in this Study.** The following components are of specific relevance:

1. The registry/database consists of four main components and will be used to identify potentially eligible patients as well as ascertain utilization and other outcomes data (see variable descriptions below). The Electronic Total Utilization Management System (**eTUMS**), a proprietary care management tool is populated by

claims data augmented by customizable care manager input; major claims events, such as hospitalization, result in automatic care manager notification. The **pharmacy claims database** accrues prescription claims daily, including drug and dose, and is downloaded to eTUMS on a weekly basis. **Laboratory claims data** are similarly downloaded on a monthly basis; laboratory reports contain the name of the test, while reports from larger laboratories also provide results. Thus these registries will provide the data necessary to measure guideline-concordant care (e.g., non-filling of mood disorder prescriptions, non-completion of cardiometabolic laboratory tests). The fourth component, **Aetna claims data**, includes use and cost data for Aim 3.

**2. The Aetna care management infrastructure is substantial and stable.** The masters level Aetna care managers who participated in the pilot will serve as the CCM care managers. They have a minimum of 5 years of care management experience with Aetna, providing short-term or ongoing care management for an average of 300 beneficiaries per year across multiple time zones and patient schedules.

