- **Patient Clinical Assessment:** During the first 10 weeks, each fourth call (monthly) will also include an assessment of overall clinical and treatment status (~15 minutes). Assessment will include the 9-item Patient Health Questionnaire (PHQ-9)(102, 103) to assess depressive symptoms, the 8-item Internal State Scale (ISS; (52, 104-106) to assess manic symptoms and well-being; medication use, adherence (7, 107), and side effects. The intake contact includes identification of care providers and recent contacts, and each follow-up call will include a focus on maintaining engagement/continuity. These calls will continue on a monthly basis for up to one year of participation, with additional phone contacts made to follow up in the event of a hospitalization or emergency room visit based on our RCTs (50-53, 108).
- **Claims Database/Registry Review:** The care manager will also use the eTUMS registry to track inpatient hospitalizations, pharmacy and laboratory status. These data, available in a clinically useful time frame (Section C.5.c), will assist the patient with trouble-shooting illness management, and assist the care manager in identifying opportunities for intervention or quality enhancement.
- **Provider communication:** Care management strategies to date have under-emphasized provider engagement (9). In the mood disorders CCM, the care manager will contact the provider at the time of patient enrollment to introduce the CCM and to determine how best to integrate CCM procedures into the provider’s practice needs. This initial contact will identify the optimal mode of communication between

provider and care manager, as well as delineation by the provider for the care manager of the expected care plan going forward (frequency of visits, medications, lab tests such as cardiometabolic monitoring). After this initial engagement and care planning contact, the care manager will contact the provider in the event of hospitalization, emergency room visit, or development of a new clinical issue, as well as to cue them if there is a crisis encounter (e.g., suicidality).

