**Table 5: Primary and Secondary Outcomes and Measures – Baseline and Follow-ups**

Aims	Key Measures	Source
Aim 1. Primary outcomes	Mood symptoms: PHQ-9	Patient survey
	Health-related quality of life-SF-12	Patient survey
Aim 1. Secondary outcomes	Guideline concordant care- key measures	Medical record (eTUMS)/claims
	Mood tx: % receiving guideline-concordant antidepressants (if unipolar depression) or guideline-concordant anti-manic treatment (bipolar disorder dx) in 6-month period	Medical record (eTUMS)/claims
	Cardiometabolic monitoring: % receiving lipid profile, fasting glucose or HbA1C	Medical record (eTUMS)/claims
	Hospitalizations (ACSC)	Aetna claims data
	Productivity (Work Limitation Questionnaire)	Patient survey
Aim 2	Organizational data: Practice demographics	Aetna data
	Patient: demographics, comorbidities	Patient survey
Aim 3:	CCM costs, patient inpatient, outpatient, ER, Rx use	Aetna claims, provider survey
	Patient utilities (SF-6)	Patient survey

**The research associate will be blind to random assignment at baseline.** In follow-ups, given the nature of the CCM intervention (CCM-2), there is the possibility that enrolled patients may inadvertently disclose their randomization status with the RA. In pilot studies we found that this is a rare occurrence, but will be mitigated through RA training (e.g., minimizing leading questions that would disclose treatment assignment).

**Primary Aim 1 (patient-level quality of life, symptoms)** include changes in mood symptoms based on the PHQ-9 (102, 103) or ISS (52, 104-106) and health quality of life via the SF-12 Mental and Physical Health Component Scores (**MCS/PCS**; 85,113).

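### The research associate's independence is contradicted, and blinding at follow-up, though intended, is weakly protected

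*Combined protocol and SAP*

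**What the plan says.** All references are to the combined protocol and SAP.

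- **Independence.** Section C.5.b, step 4, describes the RA as someone "who will be external to Aetna to maintain separation of care management and program evaluation, and will be blinded to randomization assignment". No time limit is attached to the blinding.
- **Supervision.** Section C.5.k, in the text after Figure 3, says that Aetna's Clinical Specialty Programs Head "will oversee and manage the clinical operations and fidelity of the CCM implementation, including care manager and research associate supervision".
- **Blinding by time point.** Section C.5.f, after Table 5, states: "The research associate will be blind to random assignment at baseline". For follow-up it notes that "there is the possibility that enrolled patients may inadvertently disclose their randomization status with the RA", reports that this was rare in pilot studies, and says that the risk "will be mitigated through RA training (e.g., minimizing leading questions that would disclose treatment assignment".
- **Chart access.** The text beside Figure 2 says: "Comorbidities will be ascertained from Aetna eTUMS chart reviews conducted by the RAs". Section C.5.c describes eTUMS as "claims data augmented by customizable care manager input". Section C.5.d (CCM-2) adds: "The care manager will also use the eTUMS registry to track inpatient hospitalizations, pharmacy and laboratory status".
- **Outcome collection.** Section C.5.f has the RA administer the patient survey by phone at baseline and at 6, 12, 18 and 24 months, with a mailed form as a last resort. Table 5 gives that survey as the source of both primary measures, PHQ-9 and SF-12.

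**The concern.** Patients know whether they receive care-manager calls, and their providers are not blinded either (section C5.j). The RA is therefore the main person in survey collection whose blindness can be protected. The plan recognises this by promising a blinded RA outside Aetna. That promise is undercut if the RA answers to the manager responsible for how well the intervention is delivered, or reads records in the system used to deliver it.

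At stake is the primary comparison. An interviewer who knows or guesses the arm can influence answers through tone, prompting, clarification, or persistence in reaching a patient. An effect of this kind that differs by arm would be carried into the treatment estimate, and the mixed models in section C.5.g could not separate it from a true effect. The same survey supplies work productivity and the health utilities for Aim 3.

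**Working it through.** No figure is involved, so the check sets the statements side by side.

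1. **Independence: C.5.b against C.5.k.** C.5.b gives a purpose for using an external RA: keeping care management apart from evaluation. C.5.k gives one Aetna manager responsibility for CCM operations and fidelity, and for supervising care managers and the RA alike. An RA could be employed elsewhere and still be supervised by Aetna, but the stated purpose would then fail. The two passages cannot both hold as written.

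2. **Blinding: C.5.b against C.5.f.** C.5.b is unqualified. C.5.f makes its affirmative statement for baseline, then treats later disclosure by patients as accidental and to be prevented. Accidental disclosure matters only if the RA is still meant to be blind, so the passages are compatible on intent. The weakness is that blindness at 6 to 24 months is left to be inferred. Baseline blindness does little for the treatment comparison, because baseline scores come before any intervention effect. The primary models cover change over 12 months, so blindness at the 6- and 12-month interviews matters most.

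3. **Chart access: Figure 2 text, C.5.c and C.5.d.** RAs review eTUMS charts. eTUMS takes care-manager input. Care managers work in eTUMS while delivering the CCM. It follows that a chart reviewed after the CCM starts could show activity that points to the arm. This is an inference: no section says what an RA would see. Nor does any section restrict the RA's view, mask fields, or fix when the review takes place.

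4. **Does the stated safeguard cover these routes?** The one safeguard in C.5.f is RA training, with avoidance of leading questions as its example. It addresses disclosure by the patient during a call. It does not address the reporting line or what is read in a chart.

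5. **Is there a fallback?** The analysis section (C.5.g) has no record or report of unblinding. The limitations section (C5.j) mentions unblinded providers, but not the RA's supervision or chart access.

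**The case against.** Several points on the other side deserve weight.

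- **A reader might infer that the RA is blind only at baseline.** The text does not say so. The follow-up sentences in C.5.f presuppose that blinding continues, and the pilot experience reported there was reassuring. This objection stands in full. What remains is loose specification, not abandoned blinding.
- **A reader might infer that one chart review reveals the arm.** The documents do not establish this. The comorbidity review is described alongside the initial assessment, when CCM entries may not yet exist. A care-manager entry need not identify the arm, since care managers screen and consent everyone before randomisation and Aetna also runs routine care management. The later eTUMS reviews for utilisation and cost name no reviewer. This stands against any claim of a proven leak. It does not supply the missing access or timing rule.
- **A reader might infer that Aetna supervision means an unblinded RA.** No section says that the supervisor passes on allocations. C.5.k also describes separate subcommittees for CCM implementation and for enrolment and data collection, co-chaired from the universities and Aetna. It places Aetna co-leaders' authority over Aetna personnel and provides an outside monitoring board. The RA enters data on University of Michigan systems. These arrangements reduce the risk. They do not override a sentence that assigns RA supervision explicitly.
- **PHQ-9 and SF-12 are patient-reported.** The RA does not rate the patient, and patients know their arm whatever the RA knows. This limits interviewer influence in a phone interview but does not remove it.

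**Conclusion.** The concern holds in this form. The contradiction over independence between C.5.b and C.5.k is plain from the text and needs reconciling. Blinding at follow-up is intended but not clearly stated, and it is not protected against the reporting line or chart access. The result is an avoidable risk of interviewer bias in the primary outcomes. No actual unblinding is shown.

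The size is unknown, and the documents give no basis for an estimate. It may be tempting to set a notional PHQ-9 shift against the planning effect of D=.36 in section C.5.i. That would mislead: any shift chosen would be hypothetical, and in Table 3 the .36 belongs to ISS well-being, whereas the PHQ-9 effect is -.22.

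The conclusion rests on two readings: that supervision in C.5.k means ordinary line oversight of the RA, and that RA access to eTUMS is unrestricted because no restriction is described. If either is wrong, a sentence saying so would settle that part.

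**What to change.** 1. Amend C.5.k so that the university evaluation team supervises the RA and the Aetna head's role is confined to CCM delivery, in line with C.5.b.
2. State in C.5.f that the RA stays blind at every follow-up interview (6, 12, 18 and 24 months), and keep the training as one safeguard among several.
3. Take comorbidities from a claims extract without care-manager fields, or defer RA review of eTUMS until after the patient's last interview.
4. Record each unblinding with its date and source, and report the counts by arm.

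A repeat of the primary analysis that leaves out unblinded interviews is not advisable. C.5.f links disclosure to the CCM contacts, so the exclusions would probably fall mainly in the CCM arm. They would select on a post-randomisation event and depart from the intent-to-treat principle in C.5.g.

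The cost is modest: text changes, a change to access rights or a data extract, a simple log, and some supervision time moved to the university team. If chart review is deferred, comorbidity data arrive later, which matters for any interim description of the sample but not for the final models.
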